6.5 Study intervention compliance

CCI

[REDACTED] . The date and time of each dose administered CCI [REDACTED] will be recorded in the source documents.

6.6 Dose modification

Modifications to the dose are not applicable in this study.

6.7 Continued access to study intervention after the end of the study

Continued access to VH4524184 after the end of the study is not permitted since therapeutic benefit has not yet been established.

Given the lack of longer-term clinical benefit (Section 2.3.2), ViiV Healthcare recognizes the balance between the need to conduct an early phase monotherapy clinical study (for the larger and long term unmet medical need) and the need for HIV-1 infected treatment naïve patients to receive ART as soon as possible after diagnosis. To meet both needs, this study design is efficient in screening (shortest period: approximately 7 to 14 days) and the monotherapy treatment with VH4524184 (period: 10 days). On study Day 10, following the scheduled blood collection as per SoA, participants will commence standard-of-care ART selected and prescribed by the investigator and sourced as per local requirements.

After this time, the investigator is responsible for ensuring that participants continue to receive ART, whether or not the Sponsor is providing reimbursement for post-study treatment.

The Sponsor recognizes some HIV-1 infected adults may encounter barriers to accessing ART. Where it has been determined by the Investigator to be an acceptable option, participants receiving study treatment will have the option (but are not required if no access barrier) to receive reimbursement from the Sponsor for locally marketed ARVs after the completion of the study (i.e., Day 38 EOS which includes 10 days of double-blind monotherapy and 28 days of investigator chosen SOC) for up to a maximum of 90 days. The selection of ARVs will be investigator-chosen based upon local standard of care.

6.8 Treatment of overdose

An overdose is any dose of study intervention given to a participant that exceeds the planned, randomized dose for an individual within a given dose group.

In the event of an overdose, the investigator should:

1. Evaluate the participant to determine, in consultation with the medical monitor, if possible, whether study intervention should be interrupted or whether the dose should be reduced.
2. Closely monitor the participant for any AE/SAE and laboratory abnormalities until VH4524184 can no longer be detected systemically **CCI** as medically appropriate.
3. Obtain a plasma sample for PK analysis if requested by the medical monitor (determined on a case-by-case basis).
4. Document the quantity of the excess dose as well as the duration of the overdose.

6.9 Prior and concomitant therapy

Concomitant medications (prescription and non-prescription) should be administered only as medically necessary during the study. Chemoprophylaxis for HIV-associated conditions is encouraged, if appropriate, at the discretion of the participant and their physician.

Because vaccines may cause a temporary increase in the level of HIV-1 plasma RNA, it is highly recommended that a vaccine, if necessary, be given at least 14 days prior to Screening (if an experimental vaccine, within at least 30 days prior to first dose). Please discuss with medical monitor if planning to give vaccines during this time.

Any medication or vaccine (including over-the-counter or prescription medicines, vitamins, and/or herbal supplements) that the participant is receiving at the time of enrolment or receives during the study must be recorded along with:

- Reason for use
- Dates of administration including start and end dates
- Dosage information including dose and frequency

The VH medical monitor should be contacted if there are any questions regarding concomitant or prior therapy.

6.9.1 Permitted Medications

1. Acetaminophen/paracetamol at doses of ≤ 2 g/day or NSAIDs are permitted for use any time during the study and their use documented in the CRF.
2. In the event of irritation from ECG leads, up to 2.5% topical hydrocortisone may be used at the discretion of the investigator.
3. Other concomitant medications may be considered on a case-by-case basis by the investigator in consultation with the medical monitor if required.
4. Participants must notify their Investigator of any current or proposed concomitant medication, whether prescribed or over-the counter because of the potential for interactions between such treatments and the study medications.

6.9.2 Prohibited Medications

See Section [5.2.2](#).

CCI

7 DISCONTINUATION OF STUDY INTERVENTION AND PARTICIPANT DISCONTINUATION/WITHDRAWAL

7.1 Discontinuation of study intervention

‘Discontinuation’ of study intervention refers to any participant who has not received all planned doses of the study intervention. In rare instances, it may be necessary for a participant to permanently discontinue study intervention.

If study intervention is permanently discontinued, the participant should remain in the study, continue to comply with all other aspects of the protocol (such as starting the first dose of standard of care ART on Day 10) and be followed according to the SoA (Section 1.3) to the EOS as defined in the protocol.

If participants prematurely discontinue study treatment prior to Day 10 (primary endpoint), participants may be replaced at the discretion of the Sponsor in consultation with the investigator.

Participants will not be replaced if the reason for discontinuation from the study treatment is due to a safety concern which the investigator considers reasonably attributable to study treatment e.g., when a participant meets stopping criteria. Refer to Section 7.1.2 (Liver chemistry stopping criteria), Section 7.1.3 (QTc stopping criteria) and Section 7.1.5 (Suicidal ideation and behavior) and Section 7.1.6 (Hypersensitivity reactions).

A participant may be discontinued from the study intervention at any time if any of the protocol individual stopping criteria are met:

- Emergence of any positive (abnormal) CSSRS response, or participant report of suicidal ideation and behavior at any time during the study, confirmed by the investigator or a clinician (or qualified designee) during the monotherapy period.
- Pregnancy
- \geq Grade 3 AE (or clinically significant laboratory abnormality) suspected to be related to VH4524184.
- An SAE, regardless of its severity, that is considered to be clinically significant and reasonably attributable to dosing with VH4524184, in the opinion of the Investigator.
- A grade ≥ 2 rash with concurrent fever with or without concurrent elevations in liver biochemistry reasonably attributable to dosing with VH4524184, in the opinion of the Investigator.
- Emergent medical condition that is judged by the Investigator as to jeopardize the subject’s safety if he or she continues to receive the study drug.

- Termination of the study by the Sponsor. Safety data will be reviewed by the Sponsor instream by single case and collectively. If a safety concern arises, a decision about continuation of the study will be made.
- Loss of ability to freely provide consent due to incarceration or involuntary treatment of either a psychiatric or physical (e.g., infectious disease) illness.
- Repeat non-adherence by the participant with the requirements of the protocol or treatment (as determined by Investigator in consultation with the Study Sponsor Medical Monitor)
- Clinical criteria for stopping study are met (as outlined below in Section 7.1)

7.1.1 Capturing reason for discontinuation in the eCRF

[figure not shown]
The primary reason for premature discontinuation of the study intervention will be documented in the eCRF based on the list below:

Reasons	Additional items/Sub-reasons
AE	
Lack of efficacy	
Lost to follow-up	Subject Relocated Subject was Incarcerated Other, specify Unknown
Participant Reached Protocol-Defined Stopping Criteria	Specify
Physician Decision	Specify
Pregnancy	
Protocol Deviation	Specify
Site Terminated by Sponsor	
Sponsor terminated study treatment	
Study terminated by Sponsor	
Withdrawal by Participant	Burden of Procedure Participant Relocated Pursue Alternative Treatment COVID-19 Pandemic Other
Other	Specify
Death	

7.1.2 Liver chemistry stopping criteria

Study intervention will be discontinued **for a participant** if liver chemistry stopping criteria are met:

Liver Chemistry Stopping Criteria – Liver Stopping Event Algorithm

Abbreviations: ALT = alanine transaminase; INR = international normalized ratio; SAE = serious adverse event; ULN = upper limit of normal.

Refer to Section 10.5 for required Liver Safety Actions and Follow up Assessments

Discontinuation of study intervention for abnormal liver tests is required by the investigator when a participant meets 1 of the conditions outlined in the algorithm or in the presence of abnormal liver chemistries not meeting protocol-specified stopping rules if the investigator believes that it is in best interest of the participant.

Refer to Section 8.3.7 for information about study pausing criteria.

7.1.3 QTc Stopping criteria

The Fridericia QT correction (QTcF) formula will be used in the study.

- A participant that meets either bulleted criterion based on ECG readings will be withdrawn from study treatment.
 - QTcF > 500 msec,
 - Change from baseline: QTcF > 60 msec
- The QTcF must be used for each individual participant to determine eligibility for, and discontinuation from, the study. This formula may not be changed or substituted once the participant has been enrolled.

- The QTcF stopping criteria is based on averaged QTcF values of triplicate electrocardiograms obtained over a brief (e.g., 5-10 minute) recording period.

If a clinically significant finding is identified (including, but not limited to, changes from baseline in QTcF >60 msec) after enrollment, the investigator or qualified designee will determine if any change in participant management is needed. This review of the ECG printed at the time of collection must be documented. Any new clinically relevant finding should be reported as an AE.

7.1.4 Pregnancy

Participants who become pregnant during the study should discontinue study drug. Refer to Section [8.4.5](#) for reporting requirements.

7.1.5 Suicidal ideation and behavior

Participants who experience a confirmed positive eCSSRS, or who report suicidal ideation and/or behavior at any time during the study, should have study drug withdrawn and should be referred for further medical assessment and treatment as appropriate. The participant should be encouraged to continue in the study and be followed as per the SoA (See Section [1.3](#))

See Section [8.3.6](#), Suicidal ideation and behavior risk monitoring, for additional guidance.

7.1.6 Hypersensitivity reactions Stopping Criteria

Any participant with Grade ≥ 3 allergic reactions that are considered to be possibly or probably related to the IP will be withdrawn from the study. Participants should be treated as clinically appropriate and followed until resolution of the AE.

Participants may continue IP for Grade 1 or 2 allergic reactions at the discretion of the Investigator. The participant should be advised to contact the Investigator immediately if there is any worsening of symptoms or if further systemic signs or symptoms develop. Antihistamines, topical corticosteroids, or antipruritic agents may be prescribed.

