Hypersensitivity reactions (HSR)	
Hypersensitivity is an uncommon but recognized risk for anti-retroviral regimens containing CCI [REDACTED], regardless of dose. Hypersensitivity-type reactions have been CCI [REDACTED]. These reactions were characterized by rash and constitutional findings, and sometimes organ dysfunction, including liver injury.
 
The cases which have been reported in association CCI [REDACTED] have predominantly presented within angioedema and urticaria. While a causal association with more severe or systemic hypersensitivity reactions has not been identified with CCI [REDACTED] to date, there remains a theoretical risk of such reactions with or without hepatic symptoms.
 
No events indicative of hypersensitivity were observed in Study 218803.
	
Standard Medical Monitoring practices and Clinical Safety Data Review processes including review of relevant emerging data from ongoing studies.
 
Participants with history of drug hypersensitivity, delayed-type hypersensitivity or severe hypersensitivity reactions, as well as history of hypersensitivity to the study drugs are excluded (Section 5.2).
 
Specific/detailed toxicity management guidance for HSR is included in the protocol (Section 7.1.6).
 
Informed consent forms will include notification of the potential for HSR.

CCI [REDACTED]		
Co-medications during the monotherapy phase should be limited to those that are medically necessary. Co-medications should be discussed with the ViV medical monitor.

CONFIDENTIAL

TMF-17008580
218806

Potential Risk of Clinical Significance	Summary of Data/Rationale for Risk	Mitigation Strategy
	CCI [REDACTED]	

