7.2 Participant discontinuation/withdrawal from the study

A participant may withdraw from the study at any time at the participant's own request for any reason (or without providing any reason).

A participant may be withdrawn from the study at any time at the discretion of the investigator for safety, behavioral, or adherence reasons. Discontinuing from the study for safety reasons should be infrequent.

As described in Section 7.1, participants who meet a safety stopping criteria or who discontinue study intervention due to a safety reason, should remain in the study, continue to comply with all other aspects of the protocol (such as starting the first dose of standard of care ART on Day 10) and be followed according to the SoA (Section 1.3) to the EOS as defined in the protocol.

Participants will not be replaced if the reason for discontinuation from the study is due to a safety concern.

If participants prematurely discontinue the study for non-safety reasons prior to Day 10 (primary endpoint), additional replacement participants may be enrolled at the discretion of the sponsor and investigator. These replacement participants will be assigned to the same treatment sequence and same dose as the corresponding participant who prematurely discontinued from the study.

Investigators will attempt to contact participants who do not return for scheduled visits or follow-up.

At the time of discontinuing from the study, if possible, an early discontinuation visit should be conducted, as shown in the SoA. See SoA for data to be collected at the time of study discontinuation and follow-up and for any further evaluations that need to be completed. The participant will be permanently discontinued from the study intervention and the study at that time.

All data and samples collected up to and including the date of withdrawal of/last contact with the participant will be included in the study analyses. If the participant withdraws consent for disclosure of future information, the sponsor may retain and continue to use any data collected before such a withdrawal of consent.

If a participant withdraws from the study, the participant may request destruction of any samples taken and not tested, and the investigator must document this in the site study records.

The primary reason for participant discontinuation/ withdrawal from the study will be documented in the eCRF based on the list below:

Reasons	Additional items/Sub-reasons
AE	
Lack of efficacy	

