8.4.5 Pregnancy reporting

Participants who become pregnant after the first study intervention dose must not receive subsequent doses of the study intervention but may continue other study procedures at the discretion of the investigator.

- Details of all pregnancies in female participants will be collected after the start of study treatment in the Monotherapy Period (Day 1) and until the final visit in the Follow-up Period (Day 38). Report all pregnancies to the Medical Monitor.
- If a pregnancy is reported, the investigator will record pregnancy information on the appropriate form (initial notification form or pregnancy follow-up form) and submit it to the sponsor within 24 hours of learning of the female participant's pregnancy (see Section [10.3.7](#)).
- Any pregnancy complication or elective termination of a pregnancy for medical reasons will be reported as an AE or SAE.
- Abnormal pregnancy outcomes (e.g., spontaneous abortion, fetal death, stillbirth, congenital anomalies, ectopic pregnancy) are considered SAEs and will be reported as such.
- The participant will be followed to determine the outcome of the pregnancy. The investigator will collect follow-up information on the participant and the neonate and the information will be forwarded to the sponsor. See Section [10.3.7](#) for reporting timeframes.
- Any poststudy pregnancy-related SAE considered reasonably related to the study intervention by the investigator will be reported to the sponsor as described in Section [8.4.4](#). While the investigator is not obligated to actively seek this information in former study participants, he or she may learn of an SAE through spontaneous reporting.
- All investigators are strongly encouraged to report all pregnancies exposed to standard of care ART to the Antiretroviral Pregnancy Registry (APR) as soon as the pregnancy is identified. Pregnancies can be reported to the Registry at [contact] via the data forms available at www.APRegistry.com.

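### Section 7.1.6 withdraws participants with related Grade ≥3 allergic reactions from the study, while Sections 7.1 and 7.2 stop drug only and follow them to Day 38

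*Protocol*

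**What the plan says.** Protocol Section 7.1.6 sets a mandatory rule: a participant with Grade 3 or higher allergic reactions "that are considered to be possibly or probably related to the IP will be withdrawn from the study". It then asks for follow-up until the event resolves. It does not mention the Schedule of Activities, the Day 10 ART start or Day 38.

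Section 7.1, the parent section, says: "If study intervention is permanently discontinued, the participant should remain in the study, continue to comply with all other aspects of the protocol". It names 7.1.6 among the stopping criteria for study treatment. Its own list of reasons to discontinue the intervention also covers the event, since it includes, at that grade or above, a "Grade 3 AE (or clinically significant laboratory abnormality) suspected to be related to VH4524184".

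Section 7.2 repeats the retention rule: "participants who meet a safety stopping criteria or who discontinue study intervention due to a safety reason, should remain in the study". It separately describes the early discontinuation visit for people leaving the study: "The participant will be permanently discontinued from the study intervention and the study at that time".

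The hypersensitivity row of the risk table in Section 2.3.1 points the reader to 7.1.6 for toxicity management.

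**The concern.** A site facing a severe related allergic reaction has two instructions that cannot both be followed. The risk table refers it to 7.1.6, so the study-exit sentence may well be the one it acts on.

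What is at stake is scheduled safety follow-up. The safety estimand (Protocol Section 3.2.1) handles treatment discontinuation by treatment policy, so safety data collected after the drug is stopped are meant to be used. Section 9.3.3.1 does not impute missed assessments. Liver chemistry is a secondary endpoint, and the risk table notes that hypersensitivity reactions in this setting have sometimes involved liver injury. Literal use of 7.1.6 would therefore drop scheduled liver data in participants for whom they are especially informative.

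**Working it through.** The plan states no figure to reproduce. The check compares the texts and counts visits.

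**1. Is 7.1.6 a deliberate exception?** The sibling rules under 7.1 read as follows.

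| Trigger | Action | Leaves the study? |
|---|---|---|
| Liver chemistry (7.1.2) | Study drug stopped | Not required |
| QTc (7.1.3) | "A participant that meets either bulleted criterion based on ECG readings will be withdrawn from study treatment" | Not required |
| Pregnancy (7.1.4, 8.4.5) | Study drug stopped; the participant "may continue other study procedures at the discretion of the investigator" | Not required |
| Suicidality (7.1.5) | Study drug withdrawn; participant encouraged to stay | No |
| Grade ≥3 related allergic reaction (7.1.6) | Withdrawn from the study | **Yes, mandatory** |

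Neither 7.1 nor 7.2 carves out hypersensitivity, and no rationale for an exception is given. The ordering is also inverted. A related Grade 2 rash with fever is a drug-stopping criterion in 7.1, with retention in the study, while the more severe allergic reaction ends participation. Within 7.1.6, the paragraph on Grade 1 or 2 reactions is about continuing study drug, so the natural counterpart for Grade 3 or higher is stopping drug.

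**2. What is lost under a literal reading?** Inputs from Tables 1 and 2 of the protocol:

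- Post-baseline chemistry draws: monotherapy Days 2, 4, 7, 10 = 4; standard of care Days 17, 24, 31, 38 = 4.
- Post-baseline AE reviews: monotherapy Days 2, 3, 4, 5 or 6, 7, 8 or 9, 10 = 7 (some may be by telephone); follow-up = 4.

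Assume the early discontinuation visit falls on a scheduled clinic day and supplies that day's assessments. Then lost = scheduled assessments after that day.

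| Early discontinuation visit | Liver draws lost: monotherapy + follow-up (of 8) | AE reviews lost: monotherapy + follow-up (of 11) |
|---|---|---|
| Day 2 | 3 + 4 = 7 | 6 + 4 = 10 |
| Day 4 | 2 + 4 = 6 | 4 + 4 = 8 |
| Day 7 | 1 + 4 = 5 | 2 + 4 = 6 |
| Day 10 | 0 + 4 = 4 | 0 + 4 = 4 |

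At each lost visit, one such participant takes the liver-panel n of a full active group from 6 to 6 − 1 = 5, unless an unscheduled result falls in the visit window.

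**3. What is not lost?** The early discontinuation visit includes laboratory tests, AE review and ART dispensing (Table 2). SAP Section 6.2.4 slots withdrawal-visit data into visit windows. SAP Section 4.3.2.2 counts unscheduled results towards the worst-case grade. The primary estimand already excludes HIV-1 RNA taken later than the day after discontinuation, so it barely changes. Replacement is also unaffected: a participant stopped for a related safety reason is not replaced under either reading.

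**The case against.** The best reply is that this is loose wording rather than two policies. Section 7.1.6 sits under a heading about discontinuing the intervention, 7.1 calls it a treatment-stopping criterion, and 7.2 says people who meet safety stopping criteria stay in the study. The protocol also mixes study and drug discontinuation elsewhere, for example in its replacement rules. Nor is study exit for safety foreign to the plan: 7.2 lets the investigator withdraw a participant for safety, and the retention rules say *should*. This supports the proposed correction but does not remove the conflict. The withdrawal clause in 7.2 is discretionary, and 7.2 expects safety exits to be infrequent; the rule in 7.1.6 is mandatory.

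A second reply is that the practical loss is smaller than the counts suggest. Table 2 permits extra follow-up contacts for a safety event in its early discontinuation note, Section 8.3.4 requires clinically significant abnormal results to be repeated, and the reaction itself is followed to resolution. The four draws on standard of care do not enter the monotherapy summaries. All of this stands, and it is why the point is minor.

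A third reply is that changing the pausing rule in 8.3.7 goes too far. Neighbouring rules already catch a single attributable Grade 4 event, a clinically significant attributable SAE, and systemic rash of Grade 2 or higher in two participants. The gap left is roughly two non-serious Grade 3 reactions without systemic rash. That is a fair limit on its importance, and the 7.1.6 correction does not depend on it.

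**Conclusion.** The concern holds. Section 7.1.6 contradicts 7.1 and 7.2 on whether a participant with a severe related allergic reaction stays in the study. It is wrong as written, and of minor severity.

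The cost per affected participant is 4 to 7 of 8 scheduled post-baseline liver draws and 4 to 10 of 11 AE reviews, if the site follows 7.1.6 literally and the early discontinuation visit takes place on Day 2, 4, 7 or 10. The documents give no event rate, and the risk table reports no hypersensitivity events in Study 218803, so no expected number of affected participants is claimed. The affected analyses are descriptive safety summaries.

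**What to change.** In Section 7.1.6, have the participant withdrawn from study treatment, and add that they remain in the study with follow-up per the Schedule of Activities to Day 38, citing Section 7.1.

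Make a linked edit in Section 8.3.7. The third pausing rule counts related Grade 3 or higher AEs of the same type in two or more participants only when they lead to study withdrawal, so correcting 7.1.6 alone would take these reactions out of it. Widen the rule to cover a decision either to discontinue study treatment or to withdraw from the study. Keeping both routes retains withdrawals made after dosing ends. This edit is substantive: it applies to every such AE, not just allergic reactions, and somewhat lowers the threshold for a pause review. The same gap already exists for other related Grade 3 or higher AEs that stop drug under 7.1.

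The cost is one phrase and a cross-reference in 7.1.6, and one widened phrase in 8.3.7. If the amendment is classed as substantial, it needs IRB/IEC and health authority approval (Section 10.1.1). There are no new visits and no SAP change.
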